10.3 Clinical Chemistry and Hematology Parameters

Blood samples for clinical chemistry and haematology parameters will be drawn at screening, end-of-stimulation and end-of-cycle in the fresh cycle.

10.3.1 Summary Statistics

The circulating levels of clinical chemistry and haematology parameters including change from baseline will be tabulated for each time point for each laboratory variable.

Mean change and mean percentage (%) change from baseline at each time point will be presented for each laboratory variable. In addition, descriptive statistics, i.e., the number of subjects with data, mean (standard deviation), median, minimum, and maximum values, will be presented for observed values and change from baseline at each time point for each laboratory variable.

10.3.2 Changes Relative to Normal Range

Shift tables will be prepared to compare baseline values to the end-of-stimulation and end-of-cycle values, using a categorization of low, normal and high values at each visit. Low, normal and high will be defined according to the reference ranges provided by the central laboratory.

10.3.3 Markedly Abnormal Changes

A summary table will be prepared displaying the proportion of subjects who have at least one markedly abnormal value. The table will also include a break-down by classification of the baseline value. Markedly abnormal criteria for the clinical chemistry and haematology variables are specified in Appendix 1.

10.3.4 Data Listings

All laboratory values will be listed by treatment group, subject number and time point. Values outside the reference range and markedly abnormal values will be flagged.

Laboratory variables will be grouped under "Haematology" and "Clinical Chemistry".

10.4 Injection Site Reactions

For each injection site reaction (redness, pain, itching, swelling and bruising), the number of events and number of subjects experiencing those events will be tabulated by time (immediately, 30 minutes, 24 hours), reaction type and intensity (none, mild, moderate and severe).

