5.2 Characteristics and Source of Supply

All medicinal products are provided by Ferring and will be handled according to the principles of Good Manufacturing Practice (GMP). Table 5-5 provides an overview of the presentation of each medicinal product.

Table 5-5 Characteristics of Medicinal Products

IMP / NIMP	Presentation	Manufacturer or Distributor
FE 999049	Pre-filled injection pen for multiple use containing 72 μg of FSH in 2.16 mL.	Ferring Pharmaceuticals
Placebo	Pre-filled injection pen for multiple use containing 2.16 mL of placebo.	Ferring Pharmaceuticals
GANIRELIX	Pre-filled syringe for single use delivering 250 µg of ganirelix acetate in 0.5 mL.	Merck Sharp & Dohme
NOVAREL	Vials with lyophilized powder and vials with diluent. After reconstitution, each vial delivers 5,000 IU chorionic gonadotropin.	Ferring Pharmaceuticals
LEUPROLIDE ACETATE	Vial containing 14 mg of leuprolide acetate in 2.8 mL.	Sandoz Inc.
ENDOMETRIN	Vaginal inserts of 100 mg of progesterone.	Ferring Pharmaceuticals
ESTRADIOL Tablets USP	Oral tablets of 1 mg estradiol.	Teva Pharmaceuticals USA, Inc.
PROGESTERONE Injection USP	Vial containing 500 mg of progesterone in 10 mL sesame oil solution.	West-ward Pharmaceutical Corp or Watson Pharma, Inc.

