3.1 Trial Design

3.1.1 Overall Design and Control Methods

This will be a randomized, double-blind, placebo-controlled, parallel groups, multicenter trial assessing the efficacy and safety of the rFSH preparation FE 999049 in subjects aged 35-42 years undergoing controlled ovarian stimulation for IVF / ICSI following a GnRH antagonist protocol. The primary endpoint is the cumulative ongoing pregnancy rate after the fresh cycle and cryopreserved cycles initiated within 12 months from the start of controlled ovarian stimulation. Thereby, the trial is designed to capture the clinical efficacy of a single controlled ovarian stimulation cycle in a more complete manner by following outcomes from both the fresh and subsequent cryopreserved cycles. Secondary endpoints include pharmacodynamic parameters of FSH action as well as efficacy and safety parameters related to controlled ovarian stimulation from the fresh cycle and subsequent cryopreserved cycles.

Controlled Ovarian Stimulation and Fresh Cycle

Subjects will be screened within 90 days prior to randomization for compliance with the inclusion and exclusion criteria. On day 2-3 of the menstrual cycle, subjects will be randomized in a 10:1 ratio to FE 999049 or placebo, and controlled ovarian stimulation will be initiated. FE 999049 and placebo will be self-administered subcutaneously using a pre-filled injection pen.

Subjects assigned to treatment with FE 999049 will receive a starting dose of 15 µg daily that is fixed for the first four stimulation days. Based on ovarian response, the dose may be adjusted by 3 µg, with dose increases implemented not more frequently than once every 2 days and dose decreases implemented per investigator's judgement. The minimum daily dose is 6 µg, and the maximum daily dose is 24 µg. Subjects assigned to placebo will have the injection pen dialed to the same value (dose) as if administered FE 999049. Subjects can be treated with FE 999049 or placebo for a maximum of 20 days. Coasting, use of dopamine agonist or any other drug to prevent early OHSS with the exception of GnRH agonist for triggering of final follicular maturation, are not allowed.

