Local tolerability of FE 999049 and placebo following subcutaneous administration will be assessed by the subject three times daily: immediately, 30 minutes and 24 hours after each injection. The presence and intensity of injection site reactions will be rated as none, mild, moderate or severe. The assessments will be made throughout the stimulation period and recorded by the subject in a diary.

Cryopreserved Cycles

The trial covers cryopreserved cycles initiated within 12 months from the start of controlled ovarian stimulation. Either a programmed or natural cycle can be selected for any cryopreserved cycle.

Any programmed cryopreserved cycle will be initiated within 3 days of start of menses with administration of estradiol (ESTRADIOL Tablets USP, Teva Pharmaceuticals USA, Inc.) 2 mg TID or 3 mg two times daily (BID) (or 3 mg TID at the investigator's discretion, if a daily dose of 6 mg has been shown to be insufficient in a previous cycle). If after 10-12 days of estradiol treatment the endometrial thickness is ≥ 8 mm, the subject will initiate daily intramuscular (IM) injections of 50 mg progesterone (PROGESTERONE Injection USP, West-ward Pharmaceutical Corp or Watson Pharma, Inc.) within the next 5 days in conjunction with the estradiol treatment. The ultrasound evaluation can be repeated within 7 days if the endometrial thickness criterion is not met. In programmed cryopreserved cycles, transfer of one or two blastocysts will occur on the 6th day from start of progesterone after warming and assessment of blastocyst survival and re-expansion. Subjects will have one blastocyst transferred if at least one good-quality (i.e. grade 3BB or above) blastocyst is available, or one or two blastocysts transferred if no good-quality blastocyst is available. Luteal phase support (estradiol and IM progesterone) will continue to be administered until menses, negative β hCG test, pregnancy loss or until ongoing pregnancy has been documented.

Any natural cryopreserved cycle will be initiated 7 days after start of menses with monitoring of urinary LH on a daily basis by the subject. The day after confirmation of LH surge by serum LH (local laboratory) and endometrial thickness of ≥ 8 mm, the subject will start luteal phase support with vaginal progesterone inserts (progesterone, ENDOMETRIN, Ferring Pharmaceuticals) 100 mg TID. In a

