10.1 General Considerations

Analyses for the safety analysis set will be conducted according to the actual treatment received.

Data will be presented by summary tables and listings. Categorical data will be summarized by treatment using the number and percentage of subjects in each category. For calculation of percentages, the denominator will be the total number of subjects in the respective treatment group in the safety analysis set. Continuous data will be summarized by treatment using number, mean, standard deviation, median, minimum, and maximum.

All individual subject data will be listed per subject and treatment as observed including any derived values.

Missing Data

Missing values will be treated as missing, except for causality, intensity, seriousness, and outcome of adverse events. A worst-case approach will be used: if causality is missing, the adverse event will be regarded as related to the IMP; if the intensity of an adverse event is missing, the adverse event will be regarded as severe; if seriousness is missing, the adverse event will be regarded as serious; if outcome is missing, and no date of outcome is present, the outcome is regarded as 'ongoing'.

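### Injection-site reactions are tabulated per subject with no injection denominator, although response decides how many injections each woman has and how large they are, so the by-arm display can mislead in either direction

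*SAP*

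**What the plan says.** SAP 10.4 states that, for redness, pain, itching, swelling and bruising, the event count and the "number of subjects experiencing those events will be tabulated by time", and also by "reaction type and intensity (none, mild, moderate and severe)". Protocol 9.8.2.3 plans the same display. SAP 10.1 sets the base for safety percentages: "the denominator will be the total number of subjects in the respective treatment group in the safety analysis set". Neither section plans a rate per injection or per treatment day, a common time window, or a breakdown by dose or volume.

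Subjects rate each daily injection "three times daily: immediately, 30 minutes and 24 hours after each injection" (SAP 3.1.1). In the same section, "subjects will be randomized in a 10:1 ratio to FE 999049 or placebo", with 500 and 50 planned, and "Subjects assigned to placebo will have the injection pen dialed to the same value (dose) as if administered FE 999049". The dose is 15 µg on the first four days. It may then move in 3 µg steps according to ovarian response, between 6 and 24 µg, for at most 20 days. IMP is not given after the triggering criterion is reached (protocol 5.1.1). A cycle is cancelled if, after 8 days, the investigator judges that the criterion is unlikely to be met by day 20, and in any case if it is not met after 20 days (protocol 6.1.5).

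The FE 999049 pen holds 72 µg in 2.16 mL (protocol Table 5-5). The placebo entry is "Pre-filled injection pen for multiple use containing 2.16 mL of placebo", so equal dial settings give equal volumes.

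**The concern.** The number of injections, and the volume of each, are decided after randomization by ovarian response, and response is what the active drug is meant to change. Protocol 9.1 expects cancellation for poor follicular development in about 5% of gonadotropin-exposed women, so most FE 999049 subjects should stop at triggering. It is an inference, though a natural one, that most placebo subjects will not reach two follicles of 17 mm and will stop by a different rule. A table of subjects with at least one reaction then mixes two things: how well each injection is tolerated, and how many injections were given. Raw event counts have the further problem that the arms differ tenfold in size.

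Frequency and intensity of injection-site reactions is a named secondary endpoint. Under protocol 8.4.1 a reaction becomes an adverse event only if it needs active management. The diary table therefore carries most of the evidence, and placebo is its only comparator.

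**Working it through.** **Plan's own figures.** The documents give no expected rate, precision or duration for this endpoint, so there is nothing specific to reproduce. The general safety figures for 500 subjects do reproduce: 1 − (1 − p)^500 gives 91.8%, 95.1% and 99.3% for p = 0.5%, 0.6% and 1%, and 1.96 × √(p(1 − p)/500) gives 1.9%, 2.6%, 3.1% and 3.5% for p = 5%, 10%, 15% and 20%.

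**Volume (from the documents).** 2.16/72 = 0.03 mL per dialed µg. So 6 µg is 0.18 mL, 15 µg is 0.45 mL and 24 µg is 0.72 mL.

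**Total exposure.** The two up-titrated rows use the fastest increase permitted: 15 µg on days 1-4, 18 on days 5-6, 21 on days 7-8, then 24. The responder's 9 days at 15 µg is an assumption.

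| Course | Injections | Total dialed | Total volume |
|---|---|---|---|
| Responder, 9 days at 15 µg | 9 | 9 × 15 = 135 µg | 4.05 mL |
| Non-responder cancelled after day 8 | 8 | 60 + 36 + 42 = 138 µg | 4.14 mL |
| Non-responder treated to day 20 | 20 | 138 + 12 × 24 = 426 µg | 12.78 mL |

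**Subjects with at least one reaction.** Assume the same risk p per injection in both arms and independent injections. Then P = 1 − (1 − p)^n.

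| p (assumed) | n = 8 | n = 9 | n = 20 |
|---|---|---|---|
| 0.5% | 3.9% | 4.4% | 9.5% |
| 1% | 7.7% | 8.6% | 18.2% |
| 2% | 14.9% | 16.6% | 33.2% |
| 5% | 33.7% | 37.0% | 64.2% |
| 10% | 57.0% | 61.3% | 87.8% |

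Expected events per 100 subjects are 100 × n × p. At 2% that is 16, 18 and 40. Per injection, all three groups have the same rate, 2%.

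**Masking or exaggeration.** Suppose FE 999049 is truly worse, at 3% against 2% per injection. At 9 injections it shows 1 − 0.97^9 = 24.0%. Placebo shows 33.2% at 20 injections, so the order is reversed. Placebo shows 14.9% at 8 injections, so the order is correct and the gap is slightly larger than at equal injections (24.0% against 16.6%).

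**Where the sign turns.** Let a share f of placebo subjects reach day 20 and the rest stop at day 8, with equal p. The arms balance at f = (P9 − P8)/(P20 − P8). At 2% this is 9%. Over p from 0.5% to 10% it is about 9-14% for a 9-injection responder, 17-27% for 10 injections and 26-38% for 11. The documents do not give f.

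**Clustering.** Reactions probably cluster within women. With a beta-binomial at mean risk 2% and assumed within-woman correlation ρ, P = 1 − ∏(b + i)/(s + i) for i = 0 to n − 1, where s = 1/ρ − 1 and b = 0.98s.

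| ρ (assumed) | n = 8 | n = 9 | n = 20 |
|---|---|---|---|
| 0.1 | 11.3% | 12.3% | 19.7% |
| 0.2 | 9.1% | 9.7% | 14.2% |
| 0.3 | 7.5% | 8.0% | 10.9% |

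The gaps shrink but do not vanish.

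**Days 1-4.** Both arms have four planned injections of 0.45 mL. Under independence at 2%, both show 1 − 0.98^4 = 7.8%.

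**The case against.** The table is descriptive: no test is planned, and the stated aim is to characterize safety. SAP 8.1.1 separately tabulates duration, intended and actual total dose, average daily dose, and maximum and minimum daily dose. Total reactions over total stimulation days would come close to an event rate per injection. If the rows for intensity none count assessments, the denominator is already in the table, and the table shells are in a separate document. Protocol 1.3 describes earlier injection-site reactions as low in incidence and generally mild. Making days 1-4 the main comparison would also leave out later doses and repeated exposure, although the endpoint covers the whole stimulation period.

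Much of this stands. The display is a tabulation by arm, not a formal comparison, and the days 1-4 table should be supplementary. But readers will set the two columns side by side. Separate exposure and reaction tables allow at best a crude event rate. They cannot correct the percentage of subjects with a reaction, and they do not link reactions to volume. The SAP does not say what the none rows count.

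**Conclusion.** The planned display lacks a denominator that matches how reactions arise, and it can separate the arms when tolerability per injection is equal. The illustrative size is 16.6% at 9 injections against 14.9% at 8 or 33.2% at 20. This assumes 2% risk per injection, independence and a 9-day responder; only the 20-day limit and the point after which judgement-based cancellation is possible (8 days) come from the documents. Clustering makes the gaps smaller. The volume figures are ratios of volume; no passage says that a larger volume causes more reactions.

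A reader might infer that the bias necessarily flatters FE 999049. The documents do not support that. Cancellation after 8 days can leave placebo subjects with fewer injections than responders, and no expected duration by arm is given. The offer of medication and funding for another cycle after poor response may even encourage early stopping. A reader might also infer that diary ratings lose their blinding once scans show response. That is unquantified: protocol 3.5.1 holds that poor responders to FE 999049 cannot be told apart from placebo subjects, and local estradiol for dose adjustment is optional. The point does not rest on it.

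The primary result is unaffected. This is a weakness in one secondary safety display, and it is worth a short SAP edit.

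**What to change.** In SAP 10.4:

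- Add, by arm, time point, reaction type and intensity, the percentage of IMP injections (or assessed injection-days) with each reaction, with injections given as the denominator.
- State what the rows for intensity none count: subjects, injections or assessments.
- Add a supplementary subject-level table limited to injections on stimulation days 1-4, when dialed dose, volume and planned number of injections are the same in both arms.
- Keep the existing whole-period table.

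Administration dates and daily doses (protocol 7.1.19) and reactions (protocol 7.2.3) are already recorded daily in the diary, so the cost is two extra tables, with no new data and no change in conduct. There are limits. Days 1-4 do not cover later doses or repeated exposure. A per-injection rate removes the effect of the number of injections when risk is constant, but not any effect of volume or of day of treatment. That is why the tables should be read together.

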10.5 Treatment-induced Anti-FSH Antibodies

The proportion of subjects with treatment-induced anti-FSH antibodies as well as the proportion of subjects with treatment-induced anti-FSH antibodies with neutralizing capacity will be tabulated. Furthermore, all assessments of anti-FSH antibodies will be listed for subjects with a positive result in assay 2.

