Concerning well-known risks associated with the use of gonadotropin products for controlled ovarian stimulation, subjects are closely monitored throughout the trial. The most serious risk associated with gonadotropin treatment is OHSS. OHSS manifests itself with increasing degrees of severity. Moderate/severe OHSS is associated with marked ovarian enlargement, fluid accumulation and other complications. The incidence of early OHSS can be minimized by withholding gonadotropins, withholding human chorionic gonadotropin (hCG) or administering GnRH agonist for triggering of final follicular maturation. In the current trial, a GnRH agonist will be administered for triggering of final follicular maturation in subjects who might be at risk of OHSS (as per defined criteria), and transfer in the fresh cycle will be cancelled. In addition, subjects with excessive ovarian response after triggering with hCG (as per defined criteria) will also have transfer in the fresh cycle cancelled to

Follitropin Delta, FE 999049 Solution for Injection Clinical Trial Protocol Trial Code: 000002 Date: 25 Apr 2018 E-Study Protocol-22377; Ver. 1.0

Supersedes: None Page 31 of 159

reduce the risk of late OHSS which would be amplified by pregnancy. In both instances, blastocysts will be cryopreserved. Very rare cases of serious allergic reactions have been reported after injection of gonadotropins. Concerning immunogenicity, the risk of treatment-induced anti-drug-antibodies following FE 999049 treatment is very low. In the ESTHER-1 and ESTHER-2 trials, the observed incidence of anti-FSH antibodies after treatment with FE 999049 was 1.1% in cycle 1, 0.8% in cycle 2 and 1.1% in cycle 3, which was not higher than the incidence of pre-existing anti-FSH antibodies of 1.4% before exposure of FE 999049. In all instances, titers were undetectable or very low and without neutralizing capacity. No safety or efficacy concern has been identified with regard to immunogenicity with FE 999049.

Concomitant Fertility Medications

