Clinical safety endpoints cover adverse events, clinical chemistry and hematology parameters, local tolerability, immunogenicity, OHSS and pregnancy-related events (i.e. multi-fetal gestations, biochemical pregnancies, spontaneous abortions, ectopic pregnancies and vanishing twins). Predefined local tolerability reactions, i.e. redness, pain, itching, swelling and bruising, will be assessed by the subjects on three occasions after each subcutaneous IMP injection spanning from immediately to 24 hours after. Presence of anti-FSH antibodies will be evaluated 7-10 and 21-28 days after the last administration of FE 999049 for assessment of a potential immunoglobulin M (IgM) response and a fully mounted immunoglobulin G (IgG) immune response, respectively. ¹⁵ Technical malfunction of the pens used for administration of FE 999049 and placebo will also be monitored.

Live birth is the ultimate objective for couples starting infertility treatment. Nevertheless, it can be justified to use ongoing pregnancy rate as an endpoint indicative of the final treatment outcome as few pregnancy losses occur after confirmation of ongoing pregnancy. ¹⁶ In the ESTHER-1 trial, the absolute difference between live birth rate and ongoing pregnancy rate was -0.7% among the women aged ≥35 years. In the present trial, ongoing pregnancies in the fresh and cryopreserved cycles will be followed until live birth, allowing for evaluation of cumulative live birth rate. Neonatal health data at birth, 4 weeks and 1 year after birth will be collected for infants born after the fresh cycle and cryopreserved cycles to provide additional safety information.

In conclusion, the primary and secondary endpoints are appropriate for a phase 3 trial designed to document the efficacy and safety of a gonadotropin intended for controlled ovarian stimulation.

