In subjects with a positive pre-dosing sample, a treatment-induced anti-FSH antibody response will be defined as a statistically determined fold increase in titers from the pre-dosing assessment to a post-dosing assessment.^e

All positive samples in the confirmatory assay (assay 2) will be further characterized for titer, neutralizing capacity (qualitatively and titer, if applicable) and cross-reactivity. A subject is defined to have treatment-induced anti-FSH antibodies with neutralizing capacity if she has a positive outcome of assay 4 after IMP administration and if she was negative for anti-FSH antibodies with neutralizing capacity at pre-dosing. Ferring will report treatment-induced neutralizing antibodies to the FDA.

The proportion of subjects with treatment-induced anti-FSH antibodies and the proportion of subjects with treatment-induced anti-FSH antibodies with neutralizing capacity are secondary endpoints.

Subjects with a treatment-induced anti-FSH antibody response (both with and without neutralizing capacity) will be followed until the response is negative or has returned to pre-dosing level or after a maximum of 1 year. These subjects will be called in for assessments 2 months after the last post-dosing anti-FSH antibody sampling. If required, further assessments will be made at 3, 4, 6, 9 and 12 months after the last post-dosing anti-FSH antibody sampling. The assessments will be terminated when two consecutive assessments are negative or indicate that the pre-dosing level has been reached, or after a maximum of 1 year. The assessments will also be terminated if the subject commences a new treatment cycle with any gonadotropin preparation.

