3.2 Determination of Sample Size

The proposed sample size of 550 (FE 999049:placebo = 500:50) can adequately address both the efficacy and safety objectives of the trial:

- The cumulative ongoing pregnancy rate in the FE 999049-treated subjects aged 35-42 years is estimated to be approximately 30% according to results from clinical trials conducted in the U.S.¹ By comparison, the pregnancy rate in the placebo arm is expected not to exceed 3%, the monthly spontaneous pregnancy rate in infertile women.² Therefore, the proposed sample size of 550 (FE 999049:placebo=500:50) will provide at least 99% power for the primary efficacy comparison. Based on the estimated cumulative ongoing pregnancy rate, the cumulative live birth rate from the fresh and/or cryopreserved cycles is estimated to be approximately 27%, resulting in a power for the comparison of the cumulative live birth rate to be at least 99%.
- A key pharmacodynamic parameter in subjects aged 35-42 years is cycle cancellation due to poor follicular development, which may occur in approximately 5% of the population exposed to gonadotropins.
- The safety and tolerability of daily rFSH preparations as part of an ART treatment cycle have been well documented for the population studied in previous clinical trials.^{3,4} OHSS was reported to occur in 1.7% to 3.7% of the subjects, with moderate/severe OHSS occurring in 1.4% to 2.2% of the subjects. Other adverse events were pelvic pain, pelvic discomfort and headache, with those assessed to be related to trial treatments reported in 1.5% to 7.1% of the subjects.

Table 1 shows that the planned sample size of 500 subjects exposed to FE 999049 provides a high probability to detect a rare adverse event or safety signal occurring in 0.5% or more subjects.

Incidence rate of rare event	Chance of detecting at least 1 event
0.5%	91.8%
0.6%	95.1%
1%	99.3%

Table 1Probabilities to Detect at Least One Rare Event

Table 2 presents the margin width estimates of the 95% confidence intervals for a range of adverse event rates with the planned sample size.

Adverse event rate	Margin of error width estimate
5%	1.9%
10%	2.6%
15%	3.1%
20%	3.5%

Table 2Estimated Margin Widths of 95% Confidence Intervals

4 Subject Disposition

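### Treatment-induced anti-FSH antibody incidence is diluted by women without evaluable samples, because SAP 10.5 inherits the whole-safety-set denominator of SAP 10.1

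*SAP*

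**What the plan says.** SAP 10.5 has one sentence on the estimate, which commits to tabulating two figures: "The proportion of subjects with treatment-induced anti-FSH antibodies as well as the proportion of subjects with treatment-induced anti-FSH antibodies with neutralizing capacity". It adds only a listing of all antibody assessments for women positive in assay 2. It gives no evaluability rule and no denominator. Protocol 9.8.2.4 is the same.

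SAP 10.1 supplies the default for safety percentages: "the denominator will be the total number of subjects in the respective treatment group in the safety analysis set". Protocol 9.8.1 carries the same rule. SAP 6.4 defines the safety set by randomization and exposure alone. SAP 10.1 also leaves missing safety values missing, apart from worst-case rules for four adverse-event attributes.

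The case definitions are in Protocol 7.2.4:

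- A woman negative before dosing is a case if any post-dose sample is positive in the confirmatory assay.
- A woman positive before dosing is a case on "a statistically determined fold increase in titers from the pre-dosing assessment" to a post-dose one.
- For neutralizing antibodies, assay 4 must be positive after dosing and there must have been no neutralizing antibody before it.

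The post-dose samples are due 7-10 and 21-28 days after the last dose. Protocol 3.5.2 gives their respective purposes: "for assessment of a potential immunoglobulin M (IgM) response and a fully mounted immunoglobulin G (IgG) immune response".

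**The concern.** Every route to being a case needs a comparison of a post-dose result with a pre-dose result. The denominator needs neither. A woman without a usable pair of results is never called negative, but in the percentage she has the same effect as a woman tested and found negative.

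The endpoint is a named secondary endpoint with few expected cases, and the documents compare it with low incidences from earlier trials. A reader of the table would take the percentage as incidence among women tested. SAP 10.1 also sits awkwardly with itself here, since it keeps missing values missing while dividing by everyone. Two programmers could defend different percentages from the same data.

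**Working it through.** **Inputs from the documents.** 500 women are planned on FE 999049 and 50 on placebo (SAP 3.2). Antibody incidence after FE 999049 was 1.1% in cycle 1 of the earlier phase 3 programme (Protocol 1.3).

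**Input assumed.** The share *m* of women without an evaluable pre-dose and post-dose result is not given. I use 2%, 5%, 10% and 20%.

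**The plan's own figure.** No sample size or precision is stated for antibodies. The nearest statement is that 500 exposed women "provides a high probability to detect a rare adverse event or safety signal occurring in 0.5% or more subjects". Table 1 gives 91.8% at a rate of 0.5%, and 1 − (1 − 0.005)^500 = 91.8%, so it reproduces. With 450 evaluable women the same formula gives 89.5%. That loss comes from the missing samples, not from the choice of denominator, but it is hidden unless the number evaluable is shown.

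**Direction.** Reported incidence = observed cases / N. Incidence under complete sampling = (observed cases + cases among the non-evaluable) / N. The first cannot exceed the second, whatever the reason for missing samples.

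**Size, if samples are missing at random.** Reported = true × (1 − m):

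| m | Evaluable of 500 | Whole-safety-set denominator | Evaluable denominator |
|---|---|---|---|
| 2% | 490 | 1.1% × 0.98 = 1.08% | 1.10% |
| 5% | 475 | 1.1% × 0.95 = 1.05% | 1.10% |
| 10% | 450 | 1.1% × 0.90 = 0.99% | 1.10% |
| 20% | 400 | 1.1% × 0.80 = 0.88% | 1.10% |

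In counts, 500 × 1.1% = 5.5 cases are expected. Five observed cases are 5/500 = 1.00%, against 5/475 = 1.05%, 5/450 = 1.11% or 5/400 = 1.25%. On placebo, each non-evaluable woman is 1/50 = 2% of the denominator.

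**Timing of the second sample.** Assume the last dose is the day before triggering and retrieval falls two calendar days after triggering (36 hours ± 2 hours, Protocol 6.1.6). Transfer follows five days after retrieval. Counting from the last dose:

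- Transfer: 1 + 2 + 5 = day 8.
- βhCG visit, 10-14 days after transfer: days 18 to 22.
- Required window: days 21 to 28.

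A βhCG visit 10, 11 or 12 days after transfer therefore falls on day 18, 19 or 20, before the window opens. Protocol 6.1.9.1 lists the second antibody sample at that visit. Note k of Table 6-1 calls for a separate visit when the two do not coincide. The SAP does not say how a sample taken early is to be counted.

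**The case against.** The strongest reply is that few women will be non-evaluable. Both post-dose samples are mandatory for every exposed woman (Protocol 6.1.8.2 and 6.1.9.2). Women with a cancelled cycle, no oocytes or no fresh transfer are sent to a dedicated antibody visit (6.1.5, 6.1.6). The end-of-cycle visit collects the second sample if it is outstanding, even after early discontinuation (6.1.12). For a woman negative before dosing, either post-dose sample can make her a case. Fresh cycles were complete before the COVID-19 hold, and SAP section 4 plans a listing of selected missing assessments. All of this stands. It makes the lower rows of the table more plausible than the 20% row, but it does not change the denominator rule.

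It is also true that no text imputes or classifies an untested woman as negative. The effect is arithmetic and follows from SAP 10.1, not from SAP 10.5.

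Three stronger readings are tempting, and the documents do not support them:

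- **That the fold-increase rule cannot be computed for an undetectable pre-dose titer, and so biases incidence low.** Protocol 1.3 does report of the earlier trials: "In all instances, titers were undetectable or very low and without neutralizing capacity". That covers pre-existing and post-treatment antibodies together and does not isolate pre-dose titers. The fold comes from assay validation and is to be stated in the validation report, which may also say how an undetectable titer is handled. The direction of any error depends on that convention. At the earlier 1.4% prevalence, about 7 of 500 women (500 × 1.4%) would be subject to the rule. The neutralizing definition is qualitative and does not use it.
- **That the trial-stopping consideration is affected.** Protocol 4.5 has each occurrence of neutralizing antibodies reviewed, so no proportion enters.
- **That an upper confidence limit supporting a claim of low immunogenicity is lowered.** Neither document plans an interval, threshold or test for this endpoint.

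**Conclusion.** The point holds as a modest dilution. With the denominator as written, both antibody proportions fall by the non-evaluable share. The direction is certain if any non-evaluable woman would have been a case. The size depends on an assumed share and on samples being missing at random: 1.10% becomes 1.05% at 5% missing and 0.99% at 10%. With complete sampling there is no effect. Nothing here casts doubt on the trial's primary comparison or on its handling of individual antibody-positive women. It is worth correcting because the endpoint is reported as a proportion, the expected count is five or six, and the present text allows more than one denominator.

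**What to change.** In SAP 10.5, for both proportions:

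1. Replace the SAP 10.1 denominator with safety-set women who have a valid pre-dose result and at least one valid post-dose result.
2. Report the number not evaluable in each arm, separating no pre-dose result from no post-dose result. The whole-safety-set percentage may be kept beside it.
3. Add a line restricted to women with a valid sample 21-28 days after the last dose, and state how samples taken outside that window are counted.
4. As a clarification only, cross-refer to the assay validation report for the fold threshold and for the value given to an undetectable pre-dose titer.

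Because Protocol 9.8.1 carries the same denominator rule, list the change in SAP section 14. The cost is a few sentences and one or two table rows, with no new samples or visits. The downside is a slightly less favourable reported incidence. The evaluable-set figure still assumes that missing samples are unrelated to antibody status, which is why the number not evaluable must appear with it.
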